14.2.3 Other Adverse Events

The Investigator will monitor the occurrence of adverse events for each Patient during the course of the study. All AEs will be listed on the adverse event case report forms. All pre-existing medical conditions and baseline signs and symptoms will be recorded on baseline case report forms for medical history and signs and symptoms.

Adverse events will be monitored until they are adequately resolved or explained.

14.2.4 Determination of the Relationship (Causality)

The Investigator, on the basis of his or her clinical judgment, should determine whether there is a reasonable possibility the investigational device or procedure caused or contributed to the event. Guidelines to assess AE/SAE/UADE are provided below:

Unrelated: The adverse event is determined to be solely caused by the underlying disease, disorder or condition of the patient, or attributable solely to other extraneous causes (unrelated to the device, device malfunction, or the procedure).

Possibly related: The adverse event has onset within a clinically relevant temporal relationship to exposure to the device or procedure and is plausibly at least partially caused by or aggravated by the use of the device, device malfunction, or the procedure. It must also meet one of the following criteria: (1) follows a known or easily foreseen pattern of response to device use or procedure and (2) is not fully attributable to the underlying disease, disorder or condition of the patient, or attributable to other extraneous causes.

Probably related: The adverse event has onset within a clinically relevant temporal relationship to exposure to the device or procedure and is more likely than not to be at least partially caused by or aggravated by the use of the device, device malfunction, or the procedure. It must also meet both of the following criteria: (1) follows a known or easily foreseen pattern of response to device use or procedure; and (2) is not fully attributable to the underlying disease, disorder or condition of the

CONFIDENTIAL & PROPRIETARY

patient, or attributable to other extraneous causes. In addition, if the adverse effect is reversible upon reoperation or device exchange, and such a procedure is done, the effect disappears or lessens in severity within the expected time interval.

Definitely related: The adverse event is clearly caused by the use of the device, device malfunction, or the procedure. It must meet all the following criteria: (1) has a clear temporal relationship between device exposure and onset of the event; (2) follows a known pattern of response to device use or procedure; and (3) is not reasonably attributable to the underlying disease, disorder or condition of the patient, or attributable to other extraneous causes. In addition, if the adverse effect is reversible upon reoperation or device exchange, and such a procedure is done, the effect disappears or lessens in severity within the expected time interval.

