5 PROTOCOL SYNOPSIS

| Title | Minitouch Endometrial Ablation System Treatment for Menorrhagia: An Evaluation of Safety & Effectiveness | | |
|---|---|--|--|
| Short Title | EASE Clinical Trial | | |
| IDE No. | G180282 | | |
| ClinicalTrials.gov Identifier | NCT04267562 | | |
| Protocol No. & Revision | TD18036 v5.0 | | |
| Version Date | 14Dec2021 | | |
| Study Device | Minitouch Endometrial Ablation System ("Minitouch System") | | |
| Proposed Indications for Use | The Minitouch Endometrial Ablation System is intended for ablation of the endometrial lining of the uterus for the treatment of menorrhagia (heavy menstrual bleeding) due to benign causes in premenopausal women for whom childbearing is complete | | |
| Study Design This is a prospective, multi-center, open-label, single-arm, clinical investigation study Design evaluate the Minitouch Endometrial Ablation System in premenopausal women menorrhagia menorrhagia | | | |
| Study Objective | To evaluate the safety and effectiveness of the Minitouch System | | |
| Study Duration | At least 37 months, including an estimated one month of pre-enrollment assessment and 36 months post-treatment follow up | | |
| Planned Number of Sites | Approximately 10 sites from the United States only | | |
| Planned Enrollment | Up to 126 premenopausal women with menorrhagia | | |
| Primary Effectiveness Endpoint | Percent of patients demonstrating reduction of menstrual flow as evidenced by a Pictorial Blood Loss Assessment Chart (PBLAC) score of \leq 75 at the 12-month post procedure time point | | |
| Study Success | To achieve study success, 12-month success rate should exceed the 66% Objective Performance Criterion (OPC) developed by the FDA, outlined in correspondence of Oct 29, 2015 ⁽¹⁾ | | |
| Primary Safety Measure | Reported rate of device and procedure-related serious adverse events at 12-months post-procedure as adjudicated by the CEC | | |

CONFIDENTIAL & PROPRIETARY

Page 14 of 65

Page 15 of 65

| Secondary effectiveness outcome measures include the following: | | | | |
|---|--|--|--|--|
| | DRIAC: at 6 and 12 months | | | |
| | Monstrual Status at 6 and 12 months categorized by: | | | |
| | Interstrual Status at 6 and 12 months categorized by: | | | |
| | • Amenorrhea: PBLAC score U | | | |
| | ○ Light Bleeding: PBLAC score 0 ≤ 35.0 | | | |
| | • Normal Bleeding: PBLAC score 35.1 to 75.0 | | | |
| | • Eumenorrhea: PBLAC score 75.1 to 99.9 | | | |
| | Menorrhagia: PBLAC score >100 | | | |

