14.1.4 Unanticipated Adverse Device Effects (UADEs)

Any serious adverse effect on health or safety, any life-threatening problem or death caused by, or associated with a device, if that effect, problem, or death was not previously identified in nature, severity, or degree of incidence in the application; or any other unanticipated serious problem associated with a device that relates to the rights, safety, or welfare of patients per 21 CFR 812.3 and ISO 14155.

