17.4 Analysis of Primary Safety Endpoint at 12-month

The primary safety endpoint is the rate of device or procedure-related serious adverse events. It will be evaluated 12 months post-procedure.

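### Section 14.2.4 caps a device-caused harm with no known or easily foreseen pattern at *possibly related*, so a UADE that is new in nature is under-graded in the relatedness tables

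*Combined protocol and SAP*

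**What the plan says.** Section 14.2.4 (Determination of the Relationship) tells the investigator, using clinical judgment, that he or she "should determine whether there is a reasonable possibility the investigational device or procedure caused or contributed to the event". It then gives guidelines, stated to cover AEs, SAEs and UADEs, with four grades:

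- *Unrelated*: some other cause is solely responsible.
- *Possibly related*: timing fits and the device or procedure is a plausible partial cause. In addition, "It must also meet one of the following criteria": a known or easily foreseen pattern, and incomplete attribution to other causes. The two items are joined by *and*.
- *Probably related*: timing fits and a contribution is more likely than not. In addition, "It must also meet both of the following criteria: (1) follows a known or easily foreseen pattern of response to device use or procedure", the second criterion being incomplete attribution to other causes.
- *Definitely related*: this definition opens with "The adverse event is clearly caused by the use of the device, device malfunction, or the procedure. It must meet all the following criteria". The second of the three reads "2) follows a known pattern of response to device use or procedure".

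Section 14.1.4 defines a UADE as a serious effect caused by or associated with the device that "was not previously identified in nature, severity, or degree of incidence in the application". Section 14.2.2 says adverse events will be summarized by relation to procedure and to device.

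The synopsis gives the primary safety measure as "Reported rate of device and procedure-related serious adverse events at 12-months post-procedure as adjudicated by the CEC". Section 17.4 says: "The primary safety endpoint is the rate of device or procedure-related serious adverse events". Neither these places nor sections 7.2.1 and 9.2 name the grades that count as related. Section 15 leaves the Clinical Events Committee's (CEC's) procedures to a separate charter.

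**The concern.** The strength of the evidence that a device caused an event is one question. Whether that type of event has been seen or foreseen before is another. Section 14.2.4 makes the second a precondition for a high answer to the first. The effect falls on a device-caused harm of a kind nobody anticipated, which is the kind of event that the UADE definition is partly written to capture and to which 14.2.4 says its scale applies.

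At stake is how such an event appears in the safety report. A reader of the relatedness tables would see it in the lowest related grade and take the evidence to be weak, when the grade reflects only that the event was new. There is a secondary risk to the primary safety rate if someone later takes *related* to mean only the upper grades, because the protocol does not state the cut.

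**Working it through.** No figure in the plan is in dispute. The check sets the four definitions side by side and applies them to a test case. The size of one event in the primary safety rate is then worked out.

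**Step 1. Test case.** Take an event with the right timing, clearly caused by the device, not attributable to anything else, and of a type neither known nor easily foreseen.

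| Grade | Criteria needed | Does the test case qualify? |
|---|---|---|
| Unrelated | sole other cause | No: the device caused it |
| Possibly | one of: pattern known or easily foreseen; not fully attributable elsewhere | Yes, through the second |
| Probably | both of these | No: fails the pattern criterion |
| Definitely | all of: clear timing; known pattern; not reasonably attributable elsewhere | No: fails the pattern criterion |

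The event meets the opening condition of the highest grade (clear causation) but can be given only the lowest related grade.

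**Step 2. Intermediate case.** Change one feature: the event is new but easily foreseen, for example from the mechanism. It can now reach *probably*. It still cannot reach *definitely*, because that grade asks for a known pattern and does not offer the foreseeable alternative. The ceiling at *possibly* is therefore confined to harms that are neither known nor easily foreseen.

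**Step 3. Overlap with UADEs.** Section 14.1.4 covers effects new in nature, in severity or in degree of incidence. An effect new only in severity or incidence can still follow a known pattern and reach any grade. The conflict is with the first type, new in nature.

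**Step 4. The *possibly related* wording.** The text asks for one of two criteria, then joins them with *and*. The next definition uses the same two criteria and asks for both. That contrast shows that one is enough for *possibly*, as assumed in Step 1.

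**Step 5. Size of one event.** Inputs: 126 enrolled patients (17.2.1) and an expected rate of serious procedure-related events below 1% (9.2). The expected count is below 126 × 0.01 = 1.26, so about 0 or 1 event. The rate is x/126, with exact (Clopper-Pearson) two-sided 95% limits. For x = 0 the upper limit is 1 − 0.025^(1/126) = 2.9%.

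| Related SAEs | Rate | 95% interval |
|---|---|---|
| 0 | 0% | 0 to 2.9% |
| 1 | 1/126 = 0.79% | 0.02 to 4.3% |
| 2 | 2/126 = 1.59% | 0.19 to 5.6% |

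Counting or not counting one event moves the rate by 0.79 points. With 0 or 1 event the rate stays under the 1% expectation; a second event takes it above.

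**The case against.** The best reply is that the affected class is small and the consequences limited. Table 14-1 already lists broad patterns, including tissue injury, haemorrhage, infection and cardiac complications, and section 6.1 reports over 4000 procedures outside the United States. Few serious harms would be truly novel. The grades are guidelines under clinical judgment, and the primary safety measure is adjudicated by the CEC. This stands as a limit on frequency. It does not remove the conflict: an investigator who follows the text must still under-grade the event when it occurs.

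Four stronger readings are tempting, and the documents do not support them.

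- *Novel harms drop out of the primary safety rate.* A reader might infer this from the missing cut. But 14.2.4 opens by asking about a reasonable possibility of causation, three of its four grades are named as related, and only one is not. The natural reading is that *possibly related* counts. No section limits *related* to the upper grades. The charter is not among the documents and may settle the matter.
- *The grade of one event decides the safety result.* Sections 9.2 and 17.4 set no safety hypothesis, performance goal or pass/fail limit. The figure below 1% is an expectation.
- *UADE detection is blocked.* UADE status under 14.1.4 rests on causation by or association with the device, and the reporting times in 14.3 do not depend on the grade. Section 17.5 also tabulates all reported safety events, so the event stays visible.
- *A novel harm fits no grade at all.* This needs the *possibly related* criteria to be read as both required, which the contrast with the next definition argues against.

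**Conclusion.** The point holds as a defect in the grading rule. As written, 14.2.4 prevents a device-caused harm that is neither known nor easily foreseen from rating above *possibly related*, although the scale is stated to apply to UADEs and a UADE may be new in nature. The direct consequence is an understated grade in the tables by relation to device and procedure.

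This rests on two assumptions: that those tables show the grades separately rather than collapsed into related and unrelated, and that graders follow the criteria as written. How often such an event would occur cannot be estimated from the documents; it is likely to be rare.

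For the primary safety rate there is only a risk of later ambiguity, worth about 0.8 percentage points per event at 126 patients. That part assumes the charter does not already state which grades count. The garbled *possibly related* wording is a drafting slip whose meaning can be recovered.

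**What to change.** In 14.2.4, make a known pattern supportive rather than mandatory for *probably* and *definitely related*. The criterion could read, for example: follows a known or foreseeable pattern, or the device or procedure is the most likely explanation (for *probably*) or the only explanation (for *definitely*). In the *possibly related* definition, ask for at least one of the two criteria and join them with *or*.

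In the same amendment, confirm in 9.2 and 17.4 that SAEs adjudicated as possibly, probably or definitely related count in the primary safety rate, and match this in the CEC charter.

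The cost is protocol and charter wording. A few events may receive a higher relatedness grade. No new data, patients or sample size change are needed.

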14.3 Reporting Requirements for SAEs or UADEs

It is the responsibility of the Principal Investigator to report SAEs or UADEs to the Sponsor within 24 hours of becoming aware of the SAE or UADE. Notification should occur via completion of the eCRFs. Reporting of the event to applicable regulatory bodies should occur per the established reporting criteria. For UADE reports, investigators are required to submit a report of a UADE to the Sponsor and the reviewing IRB as soon as possible, but in no event later than 10 working days after the investigator first learns of the event (§ 812.150(a)(1)). Sponsors must immediately conduct an evaluation of a UADE and must report the results of the evaluation to FDA, all reviewing IRBs, and participating investigators within 10 working days after the Sponsor first receives notice of the effect (§§ 812.46(b), 812.150(b)(1)).

14.4 Medical Treatment for AEs, SAEs and UADEs

Medical treatment for events occurring during and following the Minitouch treatment will be at the discretion of the investigator.

15 CLINICAL EVENTS COMMITTEE

A Clinical Events Committee (CEC) will be comprised of qualified multi-disciplinary individuals who are not investigators in the trial or a clinician at a trial site and who are independent of the Sponsor. The CEC is responsible for adjudicating the safety aspects of this study based on the charter . The composition, guiding policies, operating procedures and stopping rules (if safety concerns arise during their review of the study data) that govern the CEC will be described in a separate CEC Charter developed by the CEC members.

16 RISKS AND BENEFITS

16.1 Potential Risks

The potential risks and benefits of participation in this study are identified in the ICF and are to be explained to the patient prior to participating in the study. The potential risks are also summarized in the IFU. It is not anticipated that there will be any additional risks to the patient with the use of the Minitouch System that are different than those associated with current second generation GEA procedures.

16.1.1 Procedure Risks

Potential adverse events that may be associated with a second-generation GEA procedure include but are not limited to events listed in **Section 14.1.3 Anticipated Adverse Device Effects Associated with Endometrial Ablation**. With all endometrial ablation procedures, serious injury or death can occur.

Page 45 of 65

16.2 Risk Management Procedures

For several decades, endometrial ablation has been available as a treatment for HMB and subsequently, the potential risks associated with the therapy are well-known. While no new risks have been identified regarding the Minitouch System for the proposed indications for use, the following measures have been or will be taken to mitigate risk for all patients participating in the EASE Clinical Trial:

- Well-defined clinical protocol to enroll appropriate patients in the study. Specifically, eligibility criteria have been selected that exclude patients who are at higher risk for experiencing an anticipated adverse event in order to reduce the risks to patients who participate in this study.
- Close monitoring of patients will take place during the investigational procedure and throughout the study, and adverse events will be recorded in the patients' charts and on eCRFs.
- Engineering testing has been performed on the Minitouch System to help mitigate risks to the patients due to product failure.
- Investigators in this study will be selected based on their experience and competency to perform endometrial ablation and perform the research.
- Investigational device training will be conducted at each initiated study center and appropriate training records will be maintained.
- Ongoing monitoring of study data and results, including the use of an independent oversight committee: Clinical Events Committee.
- As appropriate, Sponsor or designee will be onsite to support Minitouch procedures performed under the EASE Clinical Trial protocol.

16.3 Potential Benefits

The patient may experience clinically significant relief from their menorrhagia or dysmenorrhea symptoms. There are no guaranteed additional benefits from participation in this study. Information gained from the conduct of this study may be of no benefit to others with the same medical condition.

17 STATISTICAL METHODS AND CONSIDERATIONS

The Statistical Analysis Plan (SAP) for the study will describe the data sets to be analyzed, the methods of analysis, and the specific analyses to be conducted in support of the study's primary and secondary endpoints. Those key elements are outlined below.

17.1 Analysis Cohorts

Statistical analysis will use definitions listed below.

17.1.1 Intent-to-Treat (ITT) Cohort

All patients who are enrolled in the study (enrollment defined as patients who met all study eligibility criteria and in whom the procedure is initiated) are included in the Intent-to-Treat (ITT) cohort.

The ITT cohort will be used for the following analyses (as defined in Section 9.1 & 9.2):

- Primary safety and effectiveness analyses at 12-month follow-up visits.
- Safety & effectiveness analyses at 24, and 36-month follow-up visits.

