"Since 1997, the United States Food and Drug Administration (FDA) has approved five non-hysteroscopic global endometrial ablation (GEA) devices based on the results of randomized controlled trials (RCTs) that compared the safety and effectiveness of the GEA device to the same control – hysteroscopic rollerball ablation. Rollerball ablation is an older, well-known surgical technique used to treat heavy menstrual bleeding from benign causes. The study designs that supported the approval of the five GEA devices were very similar. They enrolled between 250 and 350 subjects using either a 1:1 or 2:1 (device: control) randomization scheme and had comparable patient populations. The primary endpoint for all five studies was the reduction in menstrual blood loss measured by the Pictorial Blood Loss Assessment Chart (PBLAC), a validated menstrual blood loss scoring system. One of the inclusion criteria required a baseline PBLAC score of at least 150 or 185, and the individual patient success criteria for effectiveness was defined as a PBLAC score of less than or equal to 75 at one year following the ablation procedure. For all subjects, pretreatment evaluation was performed to confirm the study eligibility criteria were satisfied (e.g., absence of cavity distortions, lesions that might interfere with the GEA therapy). The analysis population consisted of all subjects who presented for their scheduled treatment, having satisfied the study eligibility criteria (intent-to-treat). This analysis population included women who presented for treatment, but did not receive the planned therapy due to reasons such as identification of exclusionary pathology immediately prior to ablation, withdrawal of consent, etc. Patients with missing PBLAC scores at one year following the ablation procedures were considered treatment failures. A study was considered a success if the proportion of successes in the GEA group met a pre-specified non-inferiority margin compared to the proportion of successes in the rollerball ablation control group.

Using a generalized linear mixed model with study as a random effect, the FDA determined that the average success rate across the five GEA devices was 75.6% (65.6%, 83.5%) and 77.2% (66.5%, 85.2%) for the rollerball ablation control. The FDA performed

Page 19 of 65

CONFIDENTIAL & PROPRIETARY

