10 STUDY DESIGN

This study is a prospective, multi-center, open-label, single-arm, clinical investigation to evaluate the Minitouch Endometrial Ablation System in up to 126 premenopausal women with menorrhagia. The treatment procedure may be performed in an office setting or ambulatory / outpatient surgery centers/operating room (OR).

Candidates will be identified via review of existing patient records and, if necessary, as a result of IRBapproved recruitment advertisements (see **Figure 10-1: Study Execution Diagram**). Study staff will confirm general eligibility and identify already existing SOC (standard of care) testing which may be applied to the trial.

Study staff will obtain written informed consent as outlined in Section 11.5 Informed Consent.

Screening may require more than one visit. The first visit requires documentation of written informed consent and it is recommended that the visit include patient training on the method of collecting PBLAC diary data, a validated patient self-reported menstrual diary scoring system. ⁽²⁾

A subsequent visit may occur after approximately one month, and after completion of the PBLAC diary. The subject will return the completed PBLAC diary and the site personnel will confirm menorrhagia with a PBLAC a score of \geq 150. Then the patient will continue screening for additional eligibility assessments as outlined in **Figure 10-1: Study Execution Diagram** and **Section 12.3 Screening Visits.**

Patient enrollment occurs on the day of the treatment following confirmation of eligibility. Once confirmed, then the patient may undergo the Minitouch procedure. One day after procedure, the study staff will contact the patient to assess the patient's procedure-related pelvic pain level utilizing the NRS (0-10 scale). Every effort should be made to ensure the 24-hour contact is conducted even if the window falls on a weekend. The follow-up visits will occur at 2 weeks, 3 months, 6 months and 12 months, 24 months, and 36 months post-procedure. Total study duration for a Patient is approximately 37 months, including one month of pre-enrollment assessment, and 36 months post-treatment follow up.

CONFIDENTIAL & PROPRIETARY

***NOTE:** Final eligibility must be confirmed by the investigator prior to procedure initiation.

Figure 10-1: Study Execution Diagram

Page 26 of 65

CONFIDENTIAL & PROPRIETARY

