11.9 Point of Enrollment

A consented patient will be registered into the study EDC (eCRFs) and a unique subject identification number at the time of registration will be issued via the EDC. All data will be entered in the study EDC. If a patient later declines to participate, or is excluded from enrollment, the investigator will note the reason for non-participation in the study EDC.

A patient is considered enrolled when the following milestones have occurred: (1) the ICF is signed, (2) all applicable screening has been successfully completed, and (3) all study inclusion criteria and no exclusion criteria are met. Since the final selection criteria are re-assessed prior to procedure initiation on the date

of treatment (e.g.: pregnancy test, current medications, active infections) the patient may not be enrolled until that date. Specifically, final eligibility must be confirmed by the investigator prior to initiating the Minitouch procedure.

For additional clarity, a consented patient that does not proceed to treatment for any reason (such as screen failure, declines treatment or participation), is categorized as consented-enrolled. A qualified patient in whom the Minitouch procedure is initiated is categorized as treated-enrolled.

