17.2 Analysis of Primary Efficacy Endpoint at 12-month

The primary efficacy endpoint is binary (success/failure). Success is defined as PBLAC score of \leq 75 at the 12-month follow-up assessment without incidence of additional interventions or treatments for bleeding prior to the 12-month follow-up visit. The proposed study's primary hypothesis is:

Null Hypothesis (H₀) = $p_{minitouch} \le OPC$

Alternate Hypothesis (H₁) = p_{minitouch} > OPC

where p_{minitouch} is the Minitouch Endometrial Ablation System success rate and OPC is 66% which is the FDA identified objective performance criterion (OPC) for global endometrial ablation (GEA) devices.

The exact binomial test will be conducted to compare the investigational device success rate to OPC minimum success rate for effectiveness. To achieve study success the measured success rate should exceed the 66% OPC.

ITT with imputation will be utilized to test the primary hypothesis, such that all missing data are failures for the primary endpoint. The following imputation techniques will be conducted for sensitivity analysis:

- Multiple Imputation (MI) using fully conditional specification (FCS) method, in which logistic regression is used to predict whether the missing value is likely to be a success or failure. The number of imputations will depend on the fraction of missing information.
- Tipping point, in which the numbers of successes or failures amongst missing data necessary to meet the primary endpoint hypothesis are determined.

Fisher-Freeman-Halton test will be conducted to compare the success rates between investigational sites. Results will also be stratified and compared across relevant baseline characteristics including demographics.

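### The cohort tested against the 66% OPC excludes women who present but are never started, whereas the OPC studies included them, and the protocol plans no analysis that adds them back

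*Combined protocol and SAP*

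**What the plan says.** **This trial's cohort.** Section 17.1.1 uses the ITT cohort for the 12-month primary effectiveness analysis and gives its own meaning of enrolment: "enrollment defined as patients who met all study eligibility criteria and in whom the procedure is initiated". Section 17.2 compares the success rate with 66% by an exact binomial test and adds that "ITT with imputation will be utilized to test the primary hypothesis, such that all missing data are failures for the primary endpoint". Section 11.9 labels a consented woman who does not go on to treatment as consented-enrolled. Section 12.3.3 classes women who leave before treatment starts as screen failures. Both groups are outside ITT.

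**The benchmark's cohort.** The FDA letter in Section 6 says the studies behind the OPC analysed eligible subjects who came for their scheduled treatment, and calls this intent-to-treat. It continues: "This analysis population included women who presented for treatment, but did not receive the planned therapy". Its examples are exclusionary pathology found just before ablation and withdrawal of consent. On missing data it says: "Patients with missing PBLAC scores at one year following the ablation procedures were considered treatment failures".

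**Other planned analyses.** The sensitivity analyses in Section 17.2 are multiple imputation and a tipping-point analysis for missing data. The PP cohort in Section 17.1.2 is a subset of ITT. Section 17 is an outline that refers to an SAP whose text is not in these documents.

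**Enrolment timing.** Section 10 states: "Patient enrollment occurs on the day of the treatment following confirmation of eligibility". Section 11.9 says "A patient is considered enrolled when the following milestones have occurred", and the milestones are consent, completed screening and all criteria met. Section 12.4.1 likewise enrols a woman once eligibility is confirmed, before the procedure begins.

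**The concern.** In a single-arm trial the fixed 66% is the only comparator, so the observed rate should be built as the benchmark rate was. Here the same label, intent-to-treat, covers two populations. A woman who is eligible, attends on Day 0 and is not started would have been in the denominator of the OPC studies but is absent from this trial's. If such women count as failures on the benchmark side and are left out here, the trial's rate is raised relative to 66% by an amount that no planned analysis would reveal. Adding the analysis after the results are known would be less credible than specifying it now.

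**Working it through.** **Inputs.** Null rate 66%, expected rate 78%, one-sided alpha 0.025, 114 evaluable and 126 enrolled (Section 17.2.1); exact binomial test (Section 17.2). The number of non-starts, k, is given nowhere and is assumed below.

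**1. The plan's own figure.** One-sample z test with null variance:

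n = [(1.960·√(0.66·0.34) + 0.842·√(0.78·0.22)) / 0.12]² = 113.26, so 114.

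This matches the plan. Allowing for 10% dropout, 114 × 1.1 = 125.4 gives 126, and 114/0.9 = 126.7 gives 127. The stated 126 is used from here on.

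**2. Pass mark in the initiated cohort.** For X ~ Binomial(126, 0.66), P(X ≥ 93) = 0.0374 and P(X ≥ 94) = 0.0239. The test passes at 94/126 (74.6%). For the initiated population taken by itself, its level is 2.4%, below the nominal 2.5%.

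**3. Adding k non-starts as failures.** The successes stay the same and the denominator becomes 126 + k. The p-value is P(X ≥ successes) for X ~ Binomial(126 + k, 0.66).

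| Result | Rate | One-sided p | Passes at 0.025 |
|---|---|---|---|
| 94/126 (k = 0) | 74.6% | 0.024 | yes |
| 94/127 (k = 1) | 74.0% | 0.033 | no |
| 98/126 (k = 0) | 77.8% | 0.003 | yes |
| 98/131 (k = 5) | 74.8% | 0.019 | yes |
| 98/132 (k = 6) | 74.2% | 0.026 | no |

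**4. Chance of passing when presenters are exactly at 66%.** If every non-start is a failure, the rate among initiated women is 0.66 × (126 + k)/126. The chance of passing is P(X ≥ 94) for 126 women at that rate.

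| k | Rate among initiated women | Chance of passing |
|---|---|---|
| 0 | 66.0% | 2.4% |
| 1 | 66.5% | 3.2% |
| 3 | 67.6% | 5.4% |
| 5 | 68.6% | 8.6% |

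**5. Whether another analysis closes the gap.** Multiple imputation and tipping point work on missing outcomes in the ITT test, and a non-start is not in ITT. PP removes women from ITT and adds none. Within the protocol, the gap stays open.

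**The case against.** **The group may be small or empty.** Screening already requires a biopsy and imaging or hysteroscopy. Women whose procedure is started but not completed stay in ITT and, without a 12-month PBLAC, count as failures. Since PP drops ITT women who were not treatable, ITT may already hold some untreatable women. This stands: only never-initiated presenters are at issue, and near the planned rate it takes six of them to change the result.

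**The scoring of untreated women in the OPC studies is inferred.** The letter's missing-data rule speaks of scores after the ablation procedures and does not say how never-ablated women were handled. This also stands. In addition, the OPC is the lower limit of a pooled confidence interval, so the population difference does not translate into an exact shift of 66%.

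**A presenter analysis may be in the SAP.** It may be, so the point is limited to the protocol.

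**Stronger readings that a reader might infer.**

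- *That it is unclear who is in ITT.* Sections 10, 11.9 (milestones) and 12.4.1 do time enrolment differently from Section 17.1.1. However, the definitions in Table 4-1, the clarification that closes Section 11.9, Section 12.3.3 and Section 17.1.1 all leave non-started women out. Apart from the undefined word 'initiated', membership is clear; the enrolment wording is loose.
- *That the success rule cancels the effect.* This trial also requires success "without incidence of additional interventions or treatments for bleeding prior to the 12-month follow-up visit", whereas the letter's criterion is "defined as a PBLAC score of less than or equal to 75 at one year following the ablation procedure". The letter summarises five studies in one sentence, so the documents do not show whether those studies also failed women who had further treatment. No offset can be claimed or ruled out.

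**Conclusion.** The mismatch between the tested cohort and the benchmark cohort is in the text, and the protocol plans nothing that would show its effect. Its size is unknown. It favours the device only on two assumptions: some eligible presenters are never started, and such women counted as failures in the OPC studies. On those assumptions, one non-start overturns a bare pass, six overturn 98/126, and five raise the chance of passing at a true presenter rate of 66% from 2.4% to 8.6%. With no non-starts there is no difference.

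A reader might conclude that the primary test is biased or has the wrong error rate. The documents do not support that: for the initiated population the exact test keeps its level, and no count of non-starts is given. Nor do they show that the primary cohort must change. The choice is debatable in a single-arm trial with no randomisation to protect, and a sensitivity analysis meets the need. The sample size therefore does not need restating on this account.

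**What to change.** Keep the initiated cohort as primary and make these changes:

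- Pre-specify a key sensitivity analysis of the primary test in all women who met screening eligibility and attended on Day 0 for the scheduled procedure, scoring non-starts and missing 12-month PBLAC as failures.
- Show it with and without women who fail the Day 0 eligibility recheck, because the quoted letter does not settle how they count.
- Report the number of non-starts and the reasons.
- Define 'initiated' by a named procedural step.
- Align the enrolment wording in Sections 10, 11.9 and 12.4.1 with Section 17.1.1.

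**Cost.** No new visit or procedure is needed. Reasons for non-participation already go into the EDC under Section 11.9; a Day 0 attendance flag for untreated women may have to be added. The supportive rate falls by about 0.6 points per non-start (98/126 = 77.8%, 98/127 = 77.2%). The power of the primary test does not change.
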